4.4. Exclusion Criteria

The following will exclude potential subjects from the study:

- 1. History or presence of any of the following, deemed clinically significant by the Investigator (or designee), and/or Sponsor:
 - a. liver disease
 - b. pancreatitis
 - c. peptic ulcer disease
 - d. intestinal malabsorption
 - e. cholecystectomy
 - f. gastric reduction surgery
 - g. history or presence of clinically significant cardiovascular disease:
 - i. myocardial infarction or cerebrovascular thromboembolism within 6 months prior to Day 1
 - ii. symptomatic angina pectoris within 6 months prior to Day 1
 - iii. congestive heart failure ≥ stage 2 per New York Heart Association Classification within 6 months prior to Day 1
 - iv. congenital prolonged QT syndrome
 - v. ventricular pre-excitation syndrome (Wolff-Parkinson White syndrome)
 - vi. arrhythmia (excluding benign sinus arrhythmia) or history of arrhythmia requiring medical intervention within 6 months prior to Day 1
 - vii. ventricular dysfunction or risk factors for Torsades de Pointes (eg, heart failure, cardiomyopathy, family history of Long QT Syndrome)
 - viii. ECG abnormalities that are clinically significant at Screening, Check-in (Day -1), or predose on Day 1, including, but not limited to:
 - 1. complete left bundle-branch block
 - 2. second-degree atrioventricular (AV) block, type 2, or third-degree AV block

3. QT interval corrected for heart rate (HR) using Fridericia's method (QTcF) > 450 msec

Subjects with out-of-range ECG values or abnormal ECG findings that are not clinically significant will be permitted to have ECGs repeated up to 2 times during Screening, Check-in (Day -1), and predose on Day 1 to confirm eligibility for study participation, if the repeat value(s) are normal/fall outside of the ranges stated above.

- 2. Subjects with out-of-range, at-rest (ie, supine for at least 5 minutes) vital sign measurements at Screening, Check-in (Day -1), or prior to dosing on Day 1. Out-of-range vital sign measurements are defined as:
 - a. body temperature > 37.5°C;
 - b. pulse rate < 50 or > 99 beats per minute (bpm);
 - c. systolic BP < 89 or > 139 mmHg;
 - d. diastolic BP < 50 or > 89 mmHg;
 - e. oxygen saturation < 95% (room air).

Subjects with out-of-range values for these parameters that are not clinically significant will be permitted to have vital sign measurements repeated up to 2 times during Screening, Check-in (Day -1), and predose on Day 1 to confirm eligibility for study participation if the repeat value(s) are normal/fall outside of the ranges stated above.

- 3. History or presence of clinically significant medical or psychiatric condition or disease in the opinion of the Investigator (or designee), or mentally or legally incapacitated or has significant emotional problems at the time of the Screening visit or expected during the conduct of the study.
- 4. Clinically significant abnormality, as determined by the Investigator (or designee), from physical examination at Check-in (Day -1).
- 5. Abnormal laboratory values (hematology panel, UA, clinical chemistry panel [fasted at least 8 hours]) that are clinically significant excluding those further defined in exclusion criteria #6, #7, and #8 at Screening and/or Check-in (Day -1). Subjects with out-of-range clinical laboratory results that are not clinically significant (excluding those further defined in exclusion criteria #6, #7, and #8) may have laboratory assessments repeated at the Investigator (or designee)'s discretion up to 2 times during Screening and Check-in (Day -1) to confirm eligibility for study participation if the repeat value(s) fall within normal ranges or are stabilizing.
- 6. Abnormal liver function tests (LFTs) as defined by aspartate aminotransferase, alanine aminotransferase, and serum (total and direct) bilirubin, as well as amylase, or lipase above the upper limit of the normal range per the laboratory's reference ranges at Screening or Check-in (Day -1). Subjects with out-of-range LFTs, amylase, and lipase values above the upper limit of normal that are not clinically significant will be permitted to have LFTs, amylase, or lipase assessments repeated up to 2 times during Screening and Check-in (Day -1) to confirm eligibility for study participation if the repeat value(s) fall within normal ranges.

7. Creatine kinase values above the upper limit of the normal range per the laboratory's reference ranges that are clinically significant at Screening or Check-in (Day -1). Subjects with out-of-range creatine kinase values that are not clinically significant will be permitted to have the creatine kinase assessments repeated up to 2 times during Screening and Check-in (Day -1) to confirm eligibility for study participation if the repeat value(s) are stable or normalizing.

- 8. Estimated glomerular filtration rate (eGFR) ≤ 80 mL/minute/1.73m² calculated using the CKD-EPI equation at Screening or Check-in (Day -1). Subjects with out-of-range eGFR values that are not clinically significant will be permitted to have eGFR assessments repeated up to 2 times during Screening and Check-in (Day -1) to confirm eligibility for study participation if the repeat value(s) fall above the range stated above.
- 9. HbA1c ≥ 6.5% at Screening. Subjects with out-of-range HbA1c values that are not clinically significant will be permitted to have HbA1c assessments repeated up to 2 times during Screening to confirm eligibility for study participation if the repeat value(s) fall below the range stated above.
- 10. Positive serologic test for HBsAg, HBV IgM core antibody, HCV antibody, or HIV antibody at Screening. Subjects who are positive for HBV IgM core antibody or HCV antibody require confirmation by PCR before enrollment to detect presence of active virus. Subjects who are HBV core antibody or HCV antibody positive or for whom a PCR is unable to be obtained will not be eligible.
- 11. Positive PCR test (or equivalent) for COVID-19 at Screening or Check-in (Day -1). Further details regarding COVID-19 testing (including procedures for subjects who test positive at any time throughout CRU confinement) are specified in a separate document.
- 12. History of congenital non-hemolytic hyperbilirubinemia (eg, Gilbert's syndrome).
- 13. Significant history or clinical manifestation of any allergic, dermatological, biliary, hepatic, gastrointestinal, renal, metabolic, hematological, pulmonary, cardiovascular (including any prior history of cardiomyopathy or heart failure), neurological, or psychiatric disorder (as determined by the Investigator [or designee]), or cancer within the past 5 years (except localized basal cell, squamous, or in situ cancer of the skin). Note: subjects with a history of appendectomy and/or hernia repairs will be acceptable.
- 14. History or presence, upon clinical evaluation, of any illness that, in the opinion of the Investigator (or designee), would interfere with the ability to provide informed consent or comply with study instructions, or that might confound the interpretation of the study results, or put the subject at undue risk.
- 15. History of a major surgical procedure within 30 days prior to Screening.
- 16. Known ongoing alcohol and/or drug abuse within 2 years prior to Screening, or evidence of such abuse as indicated by the laboratory assays for drugs of abuse (including cotinine and alcohol) conducted during Screening and/or at Check-in (Day -1). Tests for drugs of abuse must be negative at both Screening and Check-in (Day -1).

17. Use of tobacco, smoking-cessation products, or products containing nicotine and e-cigarettes (nicotine and non-nicotine), within 3 months prior to Screening and through EOT or ET.

- 18. Use or intention to use any prescription or over-the-counter medications (including but not limited to any moderate or strong CYP3A4 and/or CYP3A5 inhibitors or inducers [including herbal products such as St. John's wort], CYP2C8 substrates, strong P-gp inhibitors, proton pump inhibitors, antacids, H₂-receptor antagonists, and drugs that prolong QT/QTc interval, vitamin supplements, herbal products, natural or herbal supplements, and hormone-replacement therapy [HRT]) from 14 days prior to Day 1 or 5 half-lives (if known, whichever is longer [except for paracetamol/acetaminophen maximum of 2 g/day for up to 3 consecutive days during the study]) through EOT or ET, unless deemed acceptable by the Investigator (or designee) and Sponsor.
- 19. Consumption of grapefruit/grapefruit juice or Seville oranges or its juice within 7 days prior to Check-in (Day -1) and through EOT or ET.
- 20. Consumption of alcohol- or caffeine-containing foods or beverages within 72 hours prior to Check-in (Day -1) and through EOT or ET.
- 21. History of significant hypersensitivity, intolerance, or allergy to any drug compound, food, or other substance, unless approved by the Investigator (or designee).
- 22. Has been on a diet incompatible with the on-study diet, in the opinion of the Investigator (or designee), within the 30 days prior to Day 1 and through EOT or ET.
- 23. Participation in any other investigational study drug trial involving administration of any investigational drug in the past 30 days or 5 half-lives (if known), whichever is longer, prior to Day 1.
- 24. Has previously received LOXO-305 in any other study investigating LOXO-305, within 30 days prior to Day 1.
- 25. Strenuous exercise within 5 days prior to Check-in (Day -1) and through EOT or ET.
- 26. Poor peripheral venous access.
- 27. Donation of blood from 56 days prior to Screening, plasma or platelets from 4 weeks prior to Screening.
- 28. Receipt of blood products within 2 months prior to Check-in (Day -1).
- 29. Subjects who, in the opinion of the Investigator (or designee), should not participate in this study.

4.5. Subject Number and Identification

Subject numbers will consist of 6 digits in which the first set of 3 digits will identify the site and the second set of 3 digits will identify the subject (eg, 001-101).

For subjects who are withdrawn by the Investigator (or designee) or voluntarily withdraw prematurely from the study, replacement subjects will be enrolled only if deemed necessary by the Sponsor.

If necessary, as determined by the Sponsor, subjects who fail to complete the treatment or have insufficient PK data may be replaced. Replacement subjects will be assigned a subject number by adding 200 to the last 3 digits of the subject number for the subject they are replacing (eg, Subject Number 001-301 replaces Subject Number 001-101).

Subjects who are determined to be screen failures are permitted to be re-screened if the Investigator (or designee), with agreement from the Sponsor, feels that the subject may meet eligibility criteria upon re-screen. Re-screened subjects will be provided a new subject number as defined above.

4.6. Removal of Subjects from Study Participation

Subjects will be informed that they are free to withdraw from the study at any time and for any reason. The Investigator (or designee) may remove a subject from the study if, in the Investigator's (or designee's) opinion, it is not in the best interest of the subject to continue the study. Subjects may be withdrawn because of the following:

- change in compliance with inclusion/exclusion criterion that is clinically relevant and affects subject safety
- occurrence of AEs
- occurrence of pregnancy
- non-compliance with study restrictions
- intake of non-permitted concomitant medication that might affect subject safety or study assessments/objectives, etc.

Notification of withdrawal will immediately be made to the Sponsor. In case of withdrawal, efforts will be made to perform all ET assessments (Appendix 4). The date the subject is withdrawn from the study and the reason for withdrawal will be recorded on the subject's electronic Case Report Form (eCRF). All withdrawn subjects with AEs that are assessed as related to study drug and which are ongoing at ET may continue to be followed until the symptoms or value(s) return to normal, or acceptable levels, as judged by the Investigator (or designee) and confirmed by the Sponsor.

The entire study may be discontinued at the discretion of the Investigator (or designee) or Sponsor, based on the occurrence of the following:

- AEs unknown to date with respect to their nature, severity, and/or duration
- increased frequency and/or severity and/or duration of known AEs
- medical or ethical reasons affecting the continued performance of the study
- difficulties in the recruitment of subjects
- cancellation of drug development

In the event that the study is terminated early, the Sponsor or its designee will provide specific guidance to the CRU regarding the EOS procedures.

5. STUDY TREATMENTS

5.1. Description, Storage, Packaging, and Labeling

The Sponsor (or designee) will provide the Investigator (or designee) with adequate quantities of the study drug (Table 2).

Table 2: Study Drug

Study Drug	LOXO-305
Form ^a	Tablet
Strength	100 mg
Supplier	Loxo Oncology, Inc.
Manufacturer	Bend Research, Inc

^a Specific ingredients/purity will be identified in the Certificate of Analysis (or equivalent) that is supplied with the study drug(s).

The tablets containing 100 mg LOXO-305 will be supplied by the Sponsor (or designee), along with the batch/lot numbers and Certificate of Analysis. It will be provided in high-density polyethylene bottles and will be stored according to the instructions on the label.

Study drug will be stored at the CRU in a location that is locked with restricted access.

The bulk drug container and unit dose containers will be labeled in accordance with national laws and regulations. The study drug will be stored in accordance with the labeling. The study drug will be transferred from bulk supplies into the subject's dose container by qualified CRU employees. Each unit dose container will be appropriately labeled.

5.2. Study Treatment Administration

Subjects will receive each of the following treatments once throughout the study:

Treatment A

 A single oral dose of 200 mg LOXO-305 as 2 × 100 mg tablets will be administered in the morning on Day 1 or Day 8, following a fast of at least 10 hours prior to and 4 hours after dosing. Water will be restricted for 1 hour prior to and 1 hour after dosing with the exception of water administered for dose administration.

Treatment B

 A single oral dose of 200 mg LOXO-305 as 2 × 100 mg tablets will be administered in the morning on Day 1 or Day 8, approximately 30 minutes after starting a high-fat breakfast. Water will be restricted for 1 hour prior to and 1 hour after dosing with the exception of water administered for dose administration. High-fat breakfasts should be entirely consumed within 30 minutes.

Administration of LOXO-305 in Treatments A and B (on Day 1 or Day 8) should occur at approximately the same time (ie, within 15 minutes).

LOXO-305 will be administered orally with approximately 240 mL of water. Water will be restricted for 1-hour predose and 1-hour postdose, with the exception of water administered for dose administration.

Each unit dose will be prepared by qualified CRU staff.

Appropriate unit dose(s), as described above, will be administered to subjects. Although the timing of events requires that each subject will be administered the appropriate dose at a specific time, the exact dose time of subjects may be staggered to obviate the need to have all subjects on precisely the same study schedule. For each dose, the subject's actual dose time will be recorded in the source documents and transcribed into the eCRF.

Subjects will be instructed not to crush, split, or chew the study drug.

Subjects will not lay supine for 4 hours following LOXO-305 dose administration, except as necessitated by the occurrence of an AE(s) and/or study procedure(s).

5.3. Randomization

Subjects will be assigned a unique identification number upon screening. Subjects who complete the study screening assessments and meet all the eligibility criteria will be assigned a unique randomization identification number (in accordance with the requirements in Section 4.5 and the randomization scheme generated by Covance) prior to the time of the first dose, different from the screening number, and will receive the corresponding product according to the randomization scheme generated by Covance.

Subjects will receive each treatment (A and B) on one occasion. The treatments will be administered on Day 1 (Treatment A or B) and Day 8 (Treatment A or B). The sequences to be used in the randomization will be AB and BA.

5.4. Blinding

This is an open-label study.

5.5. Treatment Compliance

The following measures will be employed to ensure treatment compliance:

- All doses will be administered under the supervision of suitably qualified CRU staff.
- Immediately after oral dose administration, a visual inspection of the mouth and hands will be performed for each subject.
- At each dose preparation occasion, a predose and postdose inventory of LOXO-305 will be performed.

5.6. Drug Accountability

The Investigator (or designee) will maintain an accurate record of the receipt of LOXO-305 tablets received. In addition, an accurate drug disposition record will be kept, specifying the amount dispensed to each subject and the date of dispensing. This drug accountability record

will be available for inspection at any time. At the completion of the study, the original drug accountability record will be available for review by the Sponsor upon request.

For each batch of unit doses, the empty used unit dose containers will be discarded upon satisfactory completion of the compliance and accountability procedures. Any unused assembled unit doses will be retained until completion of the study.

At the completion of the study, all unused LOXO-305 tablets will be disposed of by the CRU, in accordance with the CRU's Standard Operating Procedures (SOPs) and local/state/federal guidelines governing waste disposal of investigational drugs, following the Sponsor's written authorization.

6. CONCOMITANT THERAPIES AND OTHER RESTRICTIONS

6.1. Concomitant Therapies

Paracetamol/acetaminophen (maximum of 2 g/day for up to 3 consecutive days) is an acceptable concomitant medication.

Subjects will refrain from participation in any other investigational study drug trial in which receipt of any investigational drug occurs within 5 half-lives (if known) or 30 days, whichever is longer, prior to Day 1.

All prescription medications and over-the-counter medications including but not limited to: moderate or strong CYP3A4 and/or CYP3A5 inhibitors or inducers (including herbal products such as St. John's wort), CYP2C8 substrates, strong P-gp inhibitors, proton pump inhibitors, antacids, H₂-receptor antagonists, and drugs that prolong QT/QTc interval, herbal products, vitamin supplements, natural or herbal supplements, and HRT are prohibited for 14 days or 5 half-lives (if known), whichever is longer (except for paracetamol/acetaminophen as referenced above), prior to Day 1 and through EOT or ET, unless deemed acceptable by the, Investigator (or designee), and Sponsor. Any medication taken by a subject during the course of the study, including details of its dosage, administration, and the reason for its use, will be documented in the eCRF.

The administration of any concomitant medication during the study is prohibited without prior approval of the Investigator (or designee) and Sponsor, unless its use is deemed necessary in a medical emergency. In this case, the use of the concomitant medication will be reported as soon as is practical.

6.2. Diet, Fluid, and Activity Control

Subjects are required to refrain from use of tobacco, smoking-cessation products, and nicotine-containing products and e-cigarettes (nicotine and non-nicotine), within 3 months prior to Screening through EOT or ET.

Consumption of foods or beverages containing grapefruit/grapefruit juice or Seville oranges or its juice within 7 days prior to Check-in (Day -1) and through EOT or ET will not be allowed.

Consumption of alcohol- or caffeine-containing foods or beverages within 72 hours prior to Check-in (Day -1) and through EOT or ET will not be allowed.

Subjects will refrain from strenuous exercise from 5 days prior to Check-in (Day -1) and during the period of confinement at the CRU and will otherwise maintain their normal level of physical activity through EOT or ET (ie, should not begin a new exercise program or participate in any unusually strenuous physical exertion).

In Treatment A, subjects will be fasted for at least 10 hours prior to dosing until 4 hours postdose, after which a meal will be provided. Water will be restricted for 1 hour prior to and 1 hour after dosing. In Treatment B, subjects will consume a high-fat breakfast (contents are detailed in Table 3) before dosing. Aside from the 240 mL of water to be ingested with Treatment A and Treatment B, water will be restricted for 1 hour prior to and 1 hour after

dosing. The high-fat breakfast should contain between 800 to 1000 calories (comprising approximately 150 calories from protein, 250 calories from carbohydrates, and 500 – 600 calories from fat). Subjects should start the meal 30 minutes prior to administration of LOXO-305 and eat this meal in 30 minutes or less. LOXO-305 should be administered 30 minutes after start of the meal.

Administration of LOXO-305 in Treatments A and B (on Day 1 or Day 8) should occur at approximately the same time (ie, within 5 minutes).

Table 3: High-fat Breakfast Content

High-fat Breakfast

- 2 eggs fried in butter
- 2 strips of bacon
- 2 slices of toast with butter
- 4 oz of hash brown potatoes (fried with butter)
- 8 oz (240 mL) of whole milk

While confined at the CRU, subjects will receive a standard diet at scheduled times that do not conflict with other study-related activities.

Fasting requirement in relation to dosing are described in Section 3.1 and Section 5.2.

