- 1. On Day 8, LOXO-305 will be administered in the morning at approximately the same time as LOXO-305 was administered on Day 1 (+/- 15 minutes), either following a fast of at least 10 hours prior to and 4 hours after LOXO-305 administration (with water restricted for 1 hour prior to and 1 hour post-LOXO-305 administration) or approximately 30 minutes after the start of a high-fat breakfast (with water restricted for 1 hour prior to and 1 hour post-LOXO-305 administration), according to the treatment sequence the subject is randomly assigned to. High-fat breakfast should be entirely consumed within 30 minutes.

- n. Clinical chemistry panel (fasted for at least 8 hours), coagulation parameters, hematology panel, and UA will be performed at Screening, Check-in (Day -1), Day 4 (72 hours postdose on Day 1), Day 7 (144 hours postdose on Day 1), Day 11 (72 hours postdose on Day 8), and Day 14 (144 hours postdose on Day 8, if the subject completes the study [EOT]), or on the day of ET. At ET or the day before EOT (Day 14), subjects are not required to be fasted prior to clinical laboratory evaluations.
- o. Testing for COVID-19 will be conducted at a minimum at Screening and Check-in (Day -1). Testing for COVID-19 may also be conducted periodically during the subject's CRU confinement, at the discretion of the Investigator (or designee). Tests will be performed by rapid polymerase chain reaction or equivalent.
- p. Urine drug screen for drugs of abuse (including cotinine) and alcohol screen (urine or breath).

CONFIDENTIAL Protocol Reference: LOXO-BTK-20009 Covance Study: 8419688

- q. Prior and concomitant medication administration will be recorded beginning at informed consent. In addition, all Investigator-approved prescription and over-the-counter medications taken by a subject within 14 days or 5 half-lives (if known), whichever is longer, prior to Day 1 will be recorded on the subject's electronic CRF.
- r. Female subjects only. Performed at Screening, Check-in (Day -1), and Day 14 (144 hours postdose on Day 8), if the subject completes the study (EOT) or on the day of ET.
- s. Post-menopausal female subjects only.

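### Does the lack of a written fast around the fed dose let uncontrolled food into the fed-versus-fasted comparison?

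*Protocol*

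**What the plan says.** For the fasted arm, Protocol Section 6.2 is explicit: "In Treatment A, subjects will be fasted for at least 10 hours prior to dosing until 4 hours postdose", with a meal provided afterwards. For the fed arm the same section says "In Treatment B, subjects will consume a high-fat breakfast (contents are detailed in Table 3) before dosing", and then "Subjects should start the meal 30 minutes prior to administration of LOXO-305 and eat this meal in 30 minutes or less". Section 5.2 gives the fed dose as "approximately 30 minutes after starting a high-fat breakfast" and adds only the water restriction.

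Appendix 4 footnotes k and l offer two alternatives, "either following a fast of at least 10 hours prior to and 4 hours after LOXO-305 administration" or dosing after the start of the breakfast, so the fast belongs to the fasted alternative alone. The synopsis, Protocol Section 3.1 and SAP Section 4 follow the same pattern.

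Two further sentences in Section 6.2 bear on the point. One is a cross-reference: "Fasting requirement in relation to dosing are described in Section 3.1 and Section 5.2". The other covers all remaining food: "While confined at the CRU, subjects will receive a standard diet at scheduled times that do not conflict with other study-related activities".

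**The concern.** The primary objective is the effect of food, with the fed condition defined by a particular high-fat, high-calorie meal. For the contrast to mean that, the breakfast should be the only planned dietary difference between the periods. As written, one arm has a food-free interval on both sides of the dose and the other has none. The cross-reference to Sections 3.1 and 5.2 does not help, because neither has a food rule for Treatment B.

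Protocol Table 1 gives a median tmax of 2 hours (range 1 to 8) at 200 mg. The peak would therefore often fall within the 4 hours that are kept food-free in Treatment A only. A snack or early meal in that interval could move Cmax in the fed arm alone. A model with sequence, period and treatment would count that movement as treatment effect, and irregular eating could also add within-subject variability.

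**Working it through.** **1. The two arms side by side** (Protocol 3.1, 5.2, 6.2 and Appendix 4; SAP 4)

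| Item | Treatment A | Treatment B |
|---|---|---|
| Food before dose | Fast, at least 10 h | Test breakfast begun 30 min before, finished within 30 min; nothing stated about earlier food |
| Food after dose | None until 4 h, then a meal | Nothing stated |
| Content of test meal | Not applicable | Table 3; 800 to 1000 calories with a stated split by protein, carbohydrate and fat |
| Water | Restricted 1 h each side, apart from dosing water | Same |
| Time of day | Morning, about the same clock time in both periods | Same |
| All other food | Scheduled standard diet in confinement | Same |

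Only two cells are open: food before the breakfast, and the time of the next meal after the fed dose. No two sections disagree, so there is no contradiction to reconcile.

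**2. Can subjects eat freely in the open intervals?** Confinement runs from Day -1 to Day 15 (Protocol 3.1), and both doses (Days 1 and 8) fall inside it. All food comes from the unit at scheduled times. The test meal is a breakfast taken shortly before a morning dose, so on an ordinary reading it is the first meal of the day and the next is a later scheduled meal. Both sequences are dosed on Days 1 and 8, so a unit following the schedule will be handling fasted and fed subjects on the same study days. These are inferences about routine; the documents do not give the clock times.

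**3. How much could another meal matter?** Two statements in the protocol are relevant.
- Section 1.4.2: in the pilot study (10 healthy volunteers, 200 mg tablets), a standard meal had little effect on the pharmacokinetics.
- Section 1.2: bioavailability of the spray-dried formulation did not depend on feeding state in dogs.

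The food at issue here would be standard unit food added to a full breakfast already eaten. The pilot did not test that combination, but it is the closest evidence in the documents.

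**4. Does the gap touch the sample size?** Inputs from Protocol 8.1: n = 20, within-subject CV 20.9%, ratio 1.05, limits 80% to 125%. SAP 8.5.3.1 gives two one-sided tests at 0.05.
- Within-subject SD on the log scale: √ln(1 + 0.209²) = 0.2068
- Standard error of the treatment difference: 0.2068 × √(2/20) = 0.0654, with 18 degrees of freedom
- Exact power: 81.2%, which reproduces the stated value of about 80%

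**5. What would a shift do?** No size for the extra food effect is given, so the multipliers below are arbitrary assumptions applied to the ratio of 1.05.

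| Multiplier | Ratio | Probability that the 90% CI lies within limits |
|---|---|---|
| 0.90 | 0.945 | 78.3% |
| 0.95 | 0.9975 | 89.8% |
| 0.98 | 1.029 | 86.8% |
| 1.00 | 1.05 | 81.2% |
| 1.02 | 1.071 | 73.1% |
| 1.05 | 1.1025 | 57.9% |
| 1.10 | 1.155 | 31.5% |

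The table shows how the equivalence test responds to a shift from any cause. It does not measure this gap, because neither the direction nor the size of a food increment is known. A higher probability produced by bias would be no gain either.

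**The case for a change.** The strongest argument for a change is that the omission is uniform and looks deliberate. Water limits are written out for both arms while food limits are written for one, and the either/or wording in Appendix 4 rules out reading the fast as shared. The 8-hour laboratory fast does not help, since no clinical laboratory panel is scheduled on Day 1 or Day 8. The protocol allows for additional sites, so a single unit's routine cannot be assumed. Eating an hour after dosing would be a deviation in Treatment A but would breach no written rule in Treatment B, so the case-by-case deviation review (Protocol 8.2, SAP 7.3) might never see it. The pilot already covered a standard meal, which makes a cleanly defined high-fat condition the particular purpose of this trial. A sentence of clarification would cost almost nothing.

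The factual part of this stands: a reader cannot confirm from the documents alone that the breakfast was the only dietary difference. The step from there to a flawed comparison does not. Unspecified food is not free access to food when subjects are confined on a scheduled diet.

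The timing argument is also limited. The tmax figures come from patients at steady state, not from single doses after a high-fat meal. tmax itself is not among the modelled parameters, and two of the three that are (AUC0-t and AUC0-inf) rest on sampling to 168 hours, so the argument bears mainly on Cmax. Added variability is asserted rather than shown: the 20.9% planning value itself comes from a food-effect crossover whose meal restrictions are not described. Requiring an identical restriction in both arms would set a new dosing condition, which is not for a statistical review to prescribe.

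**Conclusion.** The observation is accurate, but it does not call for a change. The documents leave the meal schedule around the fed dose unwritten; they do not contradict themselves, and nothing in them shows that following the plan as written would give a wrong food-effect estimate. This is missing operational detail that a clinical unit can be expected to fill sensibly.

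Any effect would fall mainly on Cmax and is probably small, but it cannot be quantified from the documents. The stated power stands at about 80%. The conclusion rests on three assumptions: that confinement and scheduled meals are observed, that the breakfast is the first meal on the dosing day, and that the pilot's finding for a standard meal is a fair guide to the effect of later standard meals.
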